In addition to the safety and PK rationale noted above, [redacted] is expected to have a greater effect on Treg expansion than the dose of [redacted] and therefore has a greater potential to benefit subjects with UC. Based on safety data review of 6 weeks of data from 5 participants from Cohort 2, the DRC may recommend progression to Cohort 3, [redacted]

[redacted]

Initial Blinded Treatment Phase

Planned Cohorts (Cohorts 1–3)

[redacted]

Enrollment in Cohorts 1-3 will occur sequentially. Progression from Cohort 1 to Cohort 2 per protocol will be based on DRC recommendations from all available unblinded safety and PK/PD data reviewed from Cohort 1 in the current study along with all available unblinded safety data [redacted]

[redacted] in a concurrent PT101 study conducted in a young adult healthy volunteer population (study MK-6194-003). Recommendations from DRC may also include modification to the study design, including but not limited to assessment of a lower dose or repeating a dose/dosing regimen, changes to subject safety monitoring assessments or addition of sampling timepoints. [redacted]

[redacted] The DRC will review all

safety and available PK/PD data from Cohort 2, and make recommendations for the next cohort (Cohort 3) regarding study continuation, dose escalation per protocol, or any modification to the study design. Moving sequentially from Cohort 1 through 3 will require demonstration of adequate safety, guided by the in-cohort stopping rules and the cohort progression criteria. At Week 12, subjects may be eligible to receive PT101 in a subsequent open-label (OL) treatment phase (non-responders only) or continue in a subsequent blinded treatment phase (responders only) for a maximum duration of up to 9 months. For subjects who do not continue into the OL or continued blinded treatment (CBT) phase, the clinic will perform a follow-up call approximately 90 days after the last dose of study drug to assess any changes in UC disease status.

Optional Cohorts (Cohorts 4–6)

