Up to 3 optional cohorts may be added following DRC review of all available data from the previous planned cohorts (Cohorts 1-3) to (a) assess additional dose levels of PT101 either in CCI and/or (b) repeat a previously studied dose level/dosing regimen. The purpose of these optional cohorts is to assess the range of doses and dosing frequency that provides optimal expansion of Tregs in the periphery while maintaining appropriate safety and tolerability. Operating principles for inclusion of optional cohorts in this study are listed below:

1. Optional cohorts will enroll subjects only after DRC recommendation and may be enrolled concurrently with the planned cohorts, if appropriate.

CCI

Definition of Dose-limiting Toxicity

A dose-limiting toxicity (DLT) is defined as any treatment-related adverse event (AE) reported within 4 weeks from dosing that meets both of the following criteria:

- Grade 3 or higher in severity according to the National Cancer Institute (NCI) Common Terminology Criteria for Adverse Events (CTCAE), Version 5.0
- A shift of ≥ 2 NCI CTCAE grades from baseline (initial presentation of the AE)

Definition of Maximum Tolerated Dose

Cohort-Progression Criteria

Cohort-progression criteria will be included in the overall data package reviewed by DRC to determine whether or not investigation of a higher or more frequent dose level of PT101 ^{CCI} 

In-Cohort Stopping Rules

During a given cohort, if 3 or more subjects experience a DLT, 2 or more subjects experience similar DLTs, or 1 subject experiences a DLT of Grade 4 or higher in severity, further enrollment to the respective cohort will be paused pending DRC evaluation of all available safety, PK, PD, biomarker and measures associated with UC disease activity data. After the DRC convenes to review these data, they may recommend study continuation (with or without modification) or termination of dosing within the cohort; DRC may also recommend de-escalation to lower doses/reduced frequency dosing regimen. If dosing within a cohort is terminated, the next-lower dose may be declared the maximum tolerated dose (MTD). Alternatively, an additional cohort at an intermediate dose may be added to better define the MTD.

The study may be stopped at the discretion of the Sponsor based on recommendations of the DRC. All necessary measures will be taken to ensure appropriate safety follow-up for all subjects in the trial.

Continued Blinded Treatment and Open-Label Phases

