3.1.1.2 Optional Cohorts (Cohorts 4–6)

Up to 3 optional cohorts may be added following DRC review of all available data from the previous planned cohorts (Cohorts 1-3) to (a) assess additional dose levels of PT101 either in CCI and/or (b) repeat a previously studied dose level/dosing frequency that provides optimal expansion of peripheral Tregs while maintaining appropriate safety and tolerability. Operating principles for inclusion of optional cohorts in this study are listed below, and will be detailed in the DRC charter:

1. Optional cohorts will enroll subjects only after DRC recommendation and may be enrolled concurrently with the planned cohorts, if appropriate.

CCI

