3.1.1.5 In-Cohort Stopping Rules

During a given cohort, if 3 or more subjects experience a DLT, 2 or more subjects experience similar DLTs, or 1 subject experiences a DLT of Grade 4 or higher in severity, further enrollment to the respective cohort will be paused pending DRC evaluation of all available safety, PK, PD, biomarker, and UC disease activity data. After the DRC convenes to review these data, they may recommend study continuation (with or without modification) or

termination of dosing within the cohort; DRC may also recommend de-escalation to lower doses/reduced frequency dosing regimen. If dosing within a cohort is terminated, the next-lower dose may be declared the maximum tolerated dose (MTD). Alternatively, an additional cohort at an intermediate dose may be added to better define the MTD.

The study may be stopped at the discretion of the Sponsor based on recommendations of the DRC. In all cases, necessary measures will be taken to ensure appropriate safety follow-up for all subjects in the trial.

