3.1.3 Study Periods

The study will be conducted as follows:

- **Screening Period:** will begin when the informed consent form (ICF) is signed. During this period, a subject will undergo baseline assessments to determine eligibility for study participation. Endoscopy (flexible sigmoidoscopy or colonoscopy as indicated)

will be performed, a stool sample will be collected, and additional disease assessment tools will be completed. The screening period will last approximately 4 weeks (\pm 1 week); it will end after all assessments required to assess eligibility have been completed. If a subject meets all eligibility criteria, they will be offered enrollment into the study.

- **Initial Blinded Treatment Phase:** will begin on Day 1 with randomization and the first dose of study drug (PT101 or placebo) administered. The IBT phase will have a duration of 12–14 weeks ^{CCI}
[REDACTED]
- Following completion of the IBT phase, subjects who are eligible may decide to enter into the 9-month CBT or OL phase.

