3.1.5 Dose Modification and Dose Schedule Deviation

If a subject has a DLT during study conduct, study drug dosing will be discontinued for that subject and the subject will be asked to return to the clinic 28 days after last dose of study drug for their ET visit. The AE triggering the DLT should be monitored through safety follow-up phone call and/or additional site visits as needed until the ET visit.

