### 3.2 TREATMENTS

Subjects in Cohorts 1 to 3 will receive placebo or PT101 at a dose of CCI CCI If optional cohorts are added based on a DRC review, no subject will receive a dose CCI

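### The DLT trigger automatically pauses only the affected cohort, so a higher-intensity cohort open at that time may go on randomising until the DRC acts

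*Protocol*

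**What the plan says.** The trigger in Protocol 3.1.1.5 is met by three or more subjects with a DLT, two or more with similar DLTs, or one DLT of Grade 4 or higher. The automatic consequence is that "further enrollment to the respective cohort will be paused pending DRC evaluation of all available safety" and other data. The synopsis uses the same scope: "further enrollment to the respective cohort will be paused pending DRC evaluation". Wider action (continuing, modifying, ending dosing in the cohort, de-escalating, stopping the study) follows DRC review. For the individual, Protocol 3.1.5 says that "study drug dosing will be discontinued for that subject".

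The overlap of cohorts is governed by these statements:

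- Planned cohorts, synopsis: "Enrollment in Cohorts 1-3 will occur sequentially".
- Opening Cohort 3, synopsis: "Based on safety data review of 6 weeks of data from 5 participants from Cohort 2, the DRC may recommend progression to Cohort 3".
- Length of treatment, 3.1.3: "The IBT phase will have a duration of 12–14 weeks".
- Optional cohorts, 3.1.1.2: after a DRC recommendation they "may be enrolled concurrently with the planned cohorts, if appropriate". They may test additional dose levels or repeat one already studied.
- Dose limit for optional cohorts, SAP 3.2: "If optional cohorts are added based on a DRC review, no subject will receive a dose", after which the text is redacted.

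**The concern.** In an ascending-dose design, a toxicity signal at one dose is also information about the doses above it. If a lower cohort reaches the plan's own threshold for holding enrolment, one would expect new subjects not to be started at a higher dose or frequency until the DRC has looked. As readable, the rule stops entry only where the signal arose. If the triggering cohort has already filled, the pause has no enrolment left to stop, although the DRC evaluation still follows.

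At stake is the exposure of newly randomised subjects in the other cohort between the trigger and the DRC's decision.

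**Working it through.** **Step 1: can a higher-intensity cohort be open when a lower one triggers?**

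- *Concurrent optional cohort.* Protocol 3.1.1.2 allows concurrent enrolment. Whether the optional cohort may be at a higher dose depends on redacted principles, so this route is conditional.
- *Cohort 3 after Cohort 2.* Cohort 3 may open on 6 weeks of data from 5 Cohort 2 participants. A cohort has at least 10 subjects and treatment lasts 12–14 weeks, so at least 10 − 5 = 5 subjects lie outside that minimum review set. Those 5 reviewed subjects may themselves have only 6 of their 12–14 weeks observed. A DLT counts if reported within 4 weeks of dosing (3.1.1.3), so Cohort 2 can still trigger after Cohort 3 has opened. Sequential enrolment does not prevent this.

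**Step 2: does other readable text hold the open cohort?**

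| Text | What it governs |
|---|---|
| Protocol 3.1.1.1 and 9.3.4: stopping rules and progression criteria guide movement from Cohort 1 to 3 | Whether the next cohort opens |
| Protocol 9.3.4 and SAP 13.1: overdose-control (EWOC) limit from the dose-toxicity model | Which dose is selected |
| Protocol 3.1.1.1: DRC may recommend closing an ongoing cohort early | Action after DRC review |
| Protocol 3.1.5: dosing stops after a DLT | The affected subject only |

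None of these automatically holds randomisation in another open cohort between trigger and DRC action.

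**Step 3: a rough illustration.** The plan gives no figure on this point. Assumptions: 8 PT101 subjects per cohort (Protocol 9.1), independent cohorts, DLT rates chosen for illustration, placebo DLTs and the Grade 4 limb not modelled. The calculation gives the chance that the lower cohort reaches *k* DLTs and the higher does not:

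P = P(Bin(8, p_low) ≥ k) × P(Bin(8, p_high) ≤ k − 1)

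For the conditioned version, suppose that the first 4 PT101 subjects (5 × 4/5 = 4 expected among 5 participants) had no DLT and contribute none later. The first factor becomes P(Bin(4, p_low) ≥ k).

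For k = 3:

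| p_low / p_high | Unconditioned | Conditioned |
|---|---|---|
| 0.05 / 0.10 | 0.0058 × 0.9619 = 0.0056 | 0.0005 × 0.9619 = 0.0005 |
| 0.10 / 0.15 | 0.0381 × 0.8948 = 0.0341 | 0.0037 × 0.8948 = 0.0033 |
| 0.15 / 0.25 | 0.1052 × 0.6785 = 0.0714 | 0.0120 × 0.6785 = 0.0081 |
| 0.20 / 0.30 | 0.2031 × 0.5518 = 0.1121 | 0.0272 × 0.5518 = 0.0150 |
| 0.25 / 0.35 | 0.3215 × 0.4278 = 0.1375 | 0.0508 × 0.4278 = 0.0217 |

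For k = 2 (every DLT counted as similar), in the same row order:

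- Unconditioned: 0.0465, 0.1228, 0.1258, 0.1268, 0.1070.
- Conditioned: 0.0114, 0.0344, 0.0402, 0.0462, 0.0443.

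The upper rows fit the plan better, since SAP 13.1 targets a toxicity probability below 10%. The unconditioned values do not require the trigger to fall after the higher cohort opens. The conditioned ones give the other 4 subjects their full risk, although some of their follow-up may already have been reviewed. Neither set measures the chance that someone is randomised between a trigger and the DRC's decision. That needs an accrual rate and a convening time, and the documents give neither.

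**The case against.** The strongest objection is redaction. Only the first operating principle for optional cohorts can be read, and Protocol 3.1.1.2 sends the detail to a DRC charter that was not available. The progression criteria, the maximum tolerated dose rules and the optional-cohort dose limit are also partly blacked out. Any of these could contain a cross-cohort hold. This stands, and it is why the point is confined to the readable text. A dose cap alone, however, would not be an enrolment hold.

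Second, the plan does link cohorts. The stopping rules guide escalation, EWOC carries low-dose toxicity into dose selection, and an unblinded DRC can recommend modification or stopping. All true, but these act when a cohort opens, when a dose is chosen or after the DRC meets.

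Third, the DRC reviews all Cohort 2 safety data, not only the 5 participants, so the Cohort 3 route is narrower than that number suggests. This stands, and it lowers the likelihood.

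A reader might infer more than the documents support in three ways:

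- *That Cohorts 1–3 randomise in parallel.* They enrol in sequence; the overlap is Cohort 3 enrolment with Cohort 2 dosing.
- *That the plan has no cross-cohort protection.* The redacted text and the charter prevent that conclusion.
- *That the binomial values are the risk to subjects.* They describe a different event.

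**Conclusion.** The point holds in limited form. On the readable text, the automatic pause covers only the triggering cohort, and a higher-intensity cohort can be open without any automatic hold until the DRC acts. The gap is confined to that interval, whose length is unknown. The likelihood is probably low, particularly near the SAP's toxicity target, and the number of subjects affected cannot be estimated.

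The conclusion rests on two assumptions: that no redacted passage or charter rule already imposes the hold and, for the optional-cohort route, that a higher dose or frequency is allowed. It is a cheap improvement to a stated rule. It does not show that the escalation scheme is unsafe.

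**What to change.** Add to Protocol 3.1.1.5 and the matching synopsis paragraph:

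*When a cohort meets the trigger, enrolment is also paused, pending DRC review, in every open cohort whose dose and dosing frequency are both at least as high as those of the triggering cohort. Where one is higher and the other lower, the cohorts are compared on planned total dose per 4 weeks, and the pause applies if the open cohort's total is at least as high.*

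The second sentence is needed because regimens that differ in both dose and interval otherwise have no clear order. Thresholds and DRC discretion after review stay as they are. If the charter already contains such a hold, state it in 3.1.1.5, where sites will see it.

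The cost is protocol and charter wording plus a setting in the randomisation system. The downside is an enrolment delay of unknown length that ends with the DRC's decision. It will occasionally be for an event in a placebo subject, because the trigger counts subjects and not PT101 subjects.

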3.1.2 Continued Blinded Treatment and Open-Label Phases

Subjects who have achieved clinical response (based on the modified Mayo Score using the endoscopic score derived by the Investigator) at Week 12 will be eligible to enter the continued blinded treatment (CBT) phase of the study. Subjects in the CBT phase will receive the same treatment allocation (PT101 or placebo) as received during the IBT phase; subjects who received PT101 will continue receiving PT101 at the same dose/regimen. Corticosteroid tapering will be initiated at Week 12 of the IBT phase for subjects entering the CBT phase.

Subjects who do not achieve clinical response at Week 12 will have the option to enter an open-label (OL) phase of the study. Subjects in the OL phase will receive PT101 at the same dose/regimen as received by subjects in their cohort during the IBT phase. Subjects participating in the OL phase who achieve a clinical response using the partial Mayo Score at Week 24 of the OL phase will also undergo corticosteroid tapering. Subjects who do not achieve a clinical response using the partial Mayo Score at Week 24 of the OL phase may continue on open-label treatment if it is considered in the best interest of the subject at the discretion of the Investigator.

Subjects with insufficient data to assess clinical response at Week 12 of IBT will not be eligible to enter the CBT or OL phases and will be discontinued from the study.

For subjects not entering the CBT or OL phases, the site will conduct a follow-up phone call approximately 48 hours after the Day 85 visit to confirm no adverse events related to study procedures had occurred.

Participation in the CBT and OL is for a maximum of 9 months.

The clinic will perform a follow-up call approximately 90 days after the last dose of study drug for all subjects in the trial (those who complete IBT only or enter the CBT or OL phase) to assess any changes in UC disease status.

3.1.3 Study Periods

The study will be conducted as follows:

- **Screening Period:** will begin when the informed consent form (ICF) is signed. During this period, a subject will undergo baseline assessments to determine eligibility for study participation. Endoscopy (flexible sigmoidoscopy or colonoscopy as indicated)

will be performed, a stool sample will be collected, and additional disease assessment tools will be completed. The screening period will last approximately 4 weeks (\pm 1 week); it will end after all assessments required to assess eligibility have been completed. If a subject meets all eligibility criteria, they will be offered enrollment into the study.

- **Initial Blinded Treatment Phase:** will begin on Day 1 with randomization and the first dose of study drug (PT101 or placebo) administered. The IBT phase will have a duration of 12–14 weeks ^{CCI}
[REDACTED]
- Following completion of the IBT phase, subjects who are eligible may decide to enter into the 9-month CBT or OL phase.

3.1.4 Early Termination or Unscheduled Visit

Subjects who receive \geq 1 dose of study drug should be encouraged to complete all study visits within the IBT phase. If subjects discontinue study drug and terminate early from the study, they will be asked to return to the study site for an early termination (ET) visit approximately 28 days after the last dose of study drug administration. If a subject has an ET visit, the assessments designated in the schedule of events (SOE) should be conducted. In addition, if at any time up to ^{CCI}
[REDACTED]

^{CCI}
[REDACTED] all procedures that were conducted at that visit will be collected in the electronic case report form (eCRF) as an unscheduled visit.

3.1.5 Dose Modification and Dose Schedule Deviation

If a subject has a DLT during study conduct, study drug dosing will be discontinued for that subject and the subject will be asked to return to the clinic 28 days after last dose of study drug for their ET visit. The AE triggering the DLT should be monitored through safety follow-up phone call and/or additional site visits as needed until the ET visit.

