- Following completion of the IBT phase, subjects who are eligible may decide to enter into the 9 -month CBT or OL phase.

Early Termination or Unscheduled Visits

Subjects who receive \geq 1 dose of study drug should be encouraged to complete all study visits within the IBT phase. If subjects discontinue study drug and terminate early from the study, they will be asked to return to the study site for an early termination (ET) visit approximately 28 days after the last dose of study drug administration. If a subject has an ET Visit, the assessments designated in the schedule of events (SOE) should be conducted. In addition, if at any time up to Study [REDACTED] CCI [REDACTED] a subject has an unscheduled study visit, all procedures that were conducted at that visit will be collected in the electronic case report form (eCRF) as an unscheduled visit.

Dose Modification and Dose Schedule Deviation

If a subject has a DLT during study conduct, study drug dosing will be discontinued for that subject and the subject will be asked to return to the clinic 28 days after last dose of study drug for their ET visit.

Study Drug Interruption Considerations

When feasible, the medical monitor should be consulted prior to study drug interruption. The medical monitor must be informed of all cases of study drug interruption for medical reasons.

Study drug interruption must occur in the following circumstances:

- Intercurrent illness that would, in the judgment of the investigator, affect assessments of clinical status to a significant degree.
- A nonserious infection (e.g., acute upper respiratory tract infection, simple urinary tract infection)
- Positive urine pregnancy test (pending confirmation of pregnancy)
- Subject is scheduled for elective or emergency surgery (excluding minor skin procedures under local or no anesthesia)

Study drug administration may be resumed only after resolution of the condition causing interruption and requires consultation with and approval by the medical monitor.

During the time of study drug interruption for any of the above, the subject may continue to have study visits and to take part in procedures and assessments if deemed medically appropriate by the investigator. Subjects with SARS-CoV 2 infection (or suspected infection) must follow local site-specific regulations and the PT101-201 COVID-19 Risk Management Plan regarding study visits and procedures.

Individual Stopping Rules

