2.2 Endpoints

2.2.1 Primary Endpoint

- Safety and tolerability as assessed by incidence of treatment-emergent adverse events (TEAEs), treatment-emergent serious adverse events (TESAEs), and changes in laboratory values, electrocardiograms (ECGs), physical exam findings, and vital signs through Week 12

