4.5.2 Subject Withdrawal From Study

A subject may be discontinued from the study for any of the following reasons:

- Completed study per protocol
- Subject withdrawal of consents including future research and genetic analysis consents*
- Study termination by sponsor
- Lost to follow-up
- Lack of compliance
- Other (as specified by the investigator)

*Any analyses in progress at the time of request for withdrawal or already performed prior to the request being received by the Sponsor will continue to be used as part of the overall research study data and results. No new analyses would be generated after the request is received. In the event that the medical records for the study are no longer available (eg, if the investigator is no longer required by regulatory authorities to retain the study records) or the specimens have been completely anonymized, there will no longer be a link between the subject's personal information and their specimens. In this situation, the request for specimen withdrawal cannot be processed.

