6.3.3 Early Termination Visit

Subjects who receive ≥ 1 dose of study drug should be encouraged to complete all study visits within the IBT phase. CCI

CCI visit will be asked to return to the study site for ET visit approximately 28 days of the last dose of study drug administration

CCI

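### The DLT rule gives every affected subject an ET visit, which conflicts with the general rule on IBT visits; separately, SAP 5.6 counts off-drug follow-up as exposure

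*Protocol*

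**What the plan says.** **The DLT rule.** Protocol Section 3.1.5 and the synopsis paragraph of the same title say: "If a subject has a DLT during study conduct, study drug dosing will be discontinued for that subject", and then "the subject will be asked to return to the clinic 28 days after last dose of study drug for their ET visit". Section 3.1.5, but not the synopsis, adds: "The AE triggering the DLT should be monitored through safety follow-up phone call and/or additional site visits as needed until the ET visit". Neither place mentions the remaining IBT visits or refers to Section 3.1.4.

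**The general rule.** Section 3.1.4 says that subjects with at least one dose "should be encouraged to complete all study visits within the IBT phase". It makes the ET visit conditional: "If subjects discontinue study drug and terminate early from the study". The synopsis paragraph just before the DLT paragraph says the same on both points. Section 6.3.3 repeats the encouragement. The start of its next sentence is redacted, and what remains is that some subjects "will be asked to return to the study site for ET visit approximately 28 days of the last dose".

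**Leaving the study.** Section 4.5.2 opens with "A subject may be discontinued from the study for any of the following reasons". A DLT is not on its list, although the list ends with an open category for the investigator.

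**The safety window.** The primary endpoint in Section 2.2.1 covers adverse events, laboratory values, ECGs, "physical exam findings, and vital signs through Week 12". Section 9.3.7 sets the same window for the primary safety analysis, and Section 6.4 places Week 12 at Day 85. Section 7.6.1.3 closes AE reporting at the later of the end-of-treatment visit and 28 days after the last treatment. After that, sites are asked only for SAEs that they judge related.

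**Exposure.** Protocol Section 9.3.7.1 asks for duration of treatment. SAP Section 5.6 calculates IBT exposure as the last IBT study visit minus the first dosing date, plus 1.

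**The concern.** A site can read Section 3.1.5 in two ways: as a 28-day safety check within continued IBT follow-up, or as the end of participation. The name of the visit, and the monitoring of the event only up to it, point to the second reading. The general rule points to the first.

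Two neighbouring sections sharpen the contrast. Section 3.1.6 says outright that subjects with interrupted drug may keep attending visits; Section 3.1.5 has no such sentence. Section 3.1.7 permanently stops drug for any attributable Grade 3 or higher event and names no ET visit. So a related Grade 3 event with a one-grade shift, which is not a DLT, falls under the general rule. A two-grade shift within 4 weeks of dosing falls under the rule that can be read as shorter follow-up.

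If a site takes ET as the end, new events between ET and Day 85, other than related SAEs, may go unrecorded, because AEs are elicited at study visits (Section 7.6.1.2). SAP Section 9.1.5 includes related events after the reporting period, but only if someone reports them. The 90-day call asks about UC status only.

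The exposure formula is a separate matter. It affects anyone who stops drug early and stays in follow-up, whatever the reason.

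**Working it through.** **Inputs.** First dose on Day 1 (Section 3.1.3). ET visit 28 days after the last dose (Section 3.1.5). Week 12 = Day 85 (Section 6.4). Dose days after Day 1 are redacted, so the later last-dose days below are assumptions.

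**Check of the plan's own figure.** With Day 1 as the first dose, Week 12 falls on 12 × 7 + 1 = Day 85, as stated.

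**Gap if a site treats ET as study exit.** With *d* the day of the last dose:

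- ET day = *d* + 28
- Gap to Day 85 = max(0, 85 − (*d* + 28)) = max(0, 57 − *d*)

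| Last dose (*d*) | ET day | Days from ET to Day 85 |
|---|---|---|
| 1 | 29 | 56 |
| 15 | 43 | 42 |
| 29 | 57 | 28 |
| 43 | 71 | 14 |
| 57 | 85 | 0 |

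A DLT after the first dose is possible, because the DLT window in Section 3.1.1.3 is 4 weeks from dosing. If IBT visits continue to Day 85, the gap is 0 for every *d*.

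**Exposure under SAP 5.6.**

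- Subject stays to Day 85: 85 − 1 + 1 = 85 days, whatever *d* is.
- Last IBT visit is the ET visit: (*d* + 28) − 1 + 1 = *d* + 28, that is 29 days for *d* = 1 and 57 for *d* = 29.
- Counted to the last dose: *d* − 1 + 1 = *d*, that is 1 day for *d* = 1 and 29 for *d* = 29.

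For a subject who stays to Day 85, the SAP figure exceeds the dose-based one by 85 − *d*: 84 days for *d* = 1 and 56 for *d* = 29. The same single dose is reported as 29 or 85 days, depending only on attendance.

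**The case against.** The strongest reply is that the protocol already answers the question. Every DLT subject has had at least one dose, so the encouragement in Sections 3.1.4 and 6.3.3 and the synopsis covers them. Section 3.1.5 stops dosing and does not order study exit. Section 6.3.4 says that even a subject who withdraws consent after dosing is to be followed for safety to end of study as far as possible, so it would be odd to release a willing DLT subject sooner. Section 7.6.1.3 also allows certain non-serious events of interest to be followed beyond the reporting period. Its cut-off depends on an end-of-treatment visit that the visible text does not define and that could fall later than ET. Finally, the condition in Section 6.3.3 and the schedule of events are redacted and may settle the matter.

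Most of this stands, and it makes continued follow-up the better supported reading. It does not remove the conflict: Section 3.1.4 gives the ET visit to subjects who stop drug and also leave the study, and the DLT paragraphs drop the second condition.

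A reader might infer that the plan ends safety follow-up for all DLT subjects and so biases the primary safety result. The documents do not support that. Section 4.5.2 does not list a DLT as a reason to leave. A DLT subject remains in the safety analysis set and already counts once as having a TEAE, a DLT and a Grade 3 or higher event, so those incidences cannot be understated. A reader might also want the share of an arm's follow-up that would be lost. That would need dose days that are redacted and a DLT count that is unknown. Section 1.3 describes only Grade 1 or 2 events in the single-dose study and no AE-related discontinuations in the ongoing healthy-volunteer study.

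On exposure, SAP Table 2 already lists days on treatment, doses given and missed doses, and Section 5.6 adds cumulative dose. A subject dosed once would therefore be recognisable. But days on treatment has no definition of its own, and the only formula given runs to the last visit.

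**Conclusion.** The conflict between the DLT paragraphs and the general rule is real but minor. Its size is at most 56 days of scheduled safety collection per affected subject. It falls by one day for each day that the last dose is later and reaches zero at Day 57. It arises only if a DLT follows an early last dose and the site takes ET as study exit. What could be lost is detail on later events and assessments in that subject, not the subject-level incidence of any TEAE, DLT or Grade 3 or higher events. Confidence is moderate, because the redacted text may already resolve it.

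The SAP 5.6 point depends on no redacted text: for a subject who stops drug early and stays in follow-up, the formula reports follow-up time as exposure. The two points belong together, because keeping DLT subjects in follow-up makes the exposure figure less accurate unless the formula also changes.

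**What to change.** **Protocol Section 3.1.5 and the synopsis DLT paragraph.** State that a DLT permanently stops study drug only; that the safety check 28 days after the last dose is kept; that the subject is encouraged to complete the remaining IBT visits through Day 85, with AEs recorded to that visit; and that the ET visit applies only to subjects who leave the study. If the redacted text already says this, a cross-reference in Section 3.1.5 is enough.

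**Protocol Section 7.6.1.3.** For these subjects, name Day 85 as the end of the reporting period when it is later than 28 days after the last dose.

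**SAP Section 5.6.** Label last IBT visit minus first dose + 1 as follow-up time. Add treatment duration as last IBT dose minus first dose + 1.

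**Cost.** A sentence or two in each protocol place, and one relabelled and one added row in the SAP. Subjects who have had a severe reaction would be asked to a few more visits, all already scheduled, which they may decline. The added events would start after the last dose, and SAP Section 9.1.5 already assigns those to the follow-up period.
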